Intervention Pilot Test. We will recruit 60 people living with HIV who are not virally suppressed and their 60 treatment partners in 1 matched-clinic pair (30 dyads/clinic) in Gaborone, Botswana. We will obtain updated data on 7 satellite clinics in the Greater Gaborone area, and match satellite clinics on number and type of staffing, number of patients total, and number of unsuppressed patients by calculating Euclidean distances between all possible pairs to determine the best (closest) matches, and then selecting one pair of matched intervention and control clinics. Clinics will be randomly assigned to standard of care or a healthcare provider guidance and treatment partner training intervention. In the randomly selected clinic over a 9-month period, (1) clinic healthcare providers will offer guidance around treatment partners to patients who are unsuppressed, in addition to patients who are initiating treatment (although we will only assess intervention effects among those who are not suppressed); and (2) the clinic will offer monthly, open treatment partner training sessions, and request that treatment partners of unsuppressed patients attend ≥ 2 sessions, one within a month after baseline, and one within 3 months after baseline. Patients and treatment partners will be asked to attend two sessions together, so that they can practice role-plays with each other: one within a month after the baseline interview, and one ~ 3 months later (as a booster session). To better fit with clinic flow and the way in which the sessions would ultimately be disseminated and implemented into clinics, the sessions will be open to all treatment partners (regardless of study enrollment) and run monthly for 9 months (during the length of time that the intervention is tested in the clinic). Each one-hour monthly open treatment partner group training session will consist of the same three components: (1) basic HIV treatment education (e.g., names and descriptions of medications and how they work, why adherence is important, how to manage side effects); (2) introduction to Motivational Interviewing (MI), why well-meaning partners can sometimes be unhelpful, how MI strategies (open questions, reflective listening) can be used to better support patients' motivation, and psychoeducation with examples of different types of treatment partner support activities that may be helpful in addition to adherence reminders; and (3) role-plays between patients and treatment partners of different types of challenging situations,

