
All patients and treatment partners will be surveyed at baseline and 3-months post-baseline, and patients' viral loads will be extracted from medical records from baseline to 6-months post-baseline. We will obtain viral load suppression rates for the intervention and control clinic at baseline and 12-months post-baseline. We will conduct an implementation process evaluation of acceptability and feasibility in the intervention clinic, using semi-structured interviews with patients and treatment partners about their experiences with attending the sessions, and healthcare providers about their experiences with intervention implementation, and suggestions for improvement.

Patients will eligible if they (1) are 18 years of age or older; (2) are on ART and initiated ART at least 6 months prior (to have sufficient time to confirm viral load); (3) are not virally suppressed (at least two viral loads ≥ 400 cp/ml within prior 12 months at time of enrollment) and do not show viral resistance in the past 6 months. Viral

load and time from ART initiation will be confirmed with clinic records before enrollment. We will recruit 80 patients (20 per clinic; half men and half women) and their 80 treatment partners. Patients will not be eligible if they screen positive for HIV-related dementia (from clinic records) and if they have not been tested for viral resistance as part of standard of care (all patients failing second-line ART and some patients failing first-line ART are undergo resistance testing). A study nurse will pre-screen patient charts and place study fliers in eligible patients' charts to remind providers to mention the study during the appointment. Interested patients will be told that they can meet with an interviewer in a private clinic space before or after the appointment or at another convenient time for an eligibility screening. Participants can be interviewed immediately after the screening or make an appointment for another time by phone or in person.

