Treatment partners will be eligible if they (1) are 18 years-old or older and (2) were selected to be the PLWH's treatment partner. Based on our pilot, we expect that some treatment partners will also be HIV-positive, and if so, patients and treatment partners may select each other as their treatment partners. For the purposes of study design, we will consider the first patient recruited to be the patient, and the patients' treatment partner to be the treatment partner (regardless of whether the treatment partner is also a patient). After patient and treatment partner participants in the intervention clinic complete the baseline interview, they will be asked to attend the next treatment partner training session (in the next month after the baseline interview), as well as in three months.

STATISTICAL ANALYSIS PLAN

Consistent with R34 guidelines, our primary purpose is to collect preliminary data on feasibility, acceptability, and outcomes; conducting formal tests of outcomes for a measure of effect size is not justified with limited sample size. Thus, the proposed analyses are meant to be exploratory, to help plan for a full RCT. We do not expect to have sufficient statistical power to adequately examine effects. We will calculate descriptive statistics and conduct bivariate analyses of intervention-control differences in change. We will use logistic regression to examine changes in viral suppression (% suppressed at follow-up, % adherent to at least 95% of doses) among enrolled patients in intervention and control clinics. We will use linear regression to examine changes in other survey outcomes (e.g., dyadic relationship support).

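### Eligibility criterion 3 does not require the latest viral load to be ≥400 cp/ml, so an already re-suppressed patient could enter and be counted as suppressed at follow-up

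*Combined protocol and SAP*

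**What the plan says.** The Study Protocol's patient eligibility paragraph sets three inclusion criteria. The third requires that patients "are not virally suppressed (at least two viral loads ≥ 400 cp/ml within prior 12 months at time of enrollment" and that they "do not show viral resistance in the past 6 months". Patients are excluded "if they have not been tested for viral resistance as part of standard of care", and the text explains that "all patients failing second-line ART and some patients failing first-line ART are undergo resistance testing". Before enrolment, viral "load and time from ART initiation will be confirmed with clinic records before enrollment"; which value is checked, and how recent it must be, is not stated.

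On data collection, the Study Protocol says that patients' "viral loads will be extracted from medical records from baseline to 6-months post-baseline". It defines no baseline viral load and no window for one.

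The Intervention Pilot Test paragraph says that providers will also guide patients who are starting treatment, "although we will only assess intervention effects among those who are not suppressed".

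The Statistical Analysis Plan uses logistic regression for changes in viral suppression. The measure is the percentage "suppressed at follow-up, % adherent to at least 95% of doses) among enrolled patients in intervention and control clinics". It also plans bivariate comparisons of change between the clinics. It names no baseline suppression status, whether as covariate, stratum or exclusion.

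**The concern.** Percentage suppressed at follow-up measures change only if everyone starts unsuppressed. Criterion 3 appears to guarantee that, but its stated test looks back over 12 months and counts high values without regard to their order. A chart with values ≥400 cp/ml at 11 and 8 months before enrolment and a value <400 at 2 months before meets the test.

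Such a patient would probably be suppressed at follow-up for reasons that pre-date the intervention. Preliminary effect on viral suppression is part of Aim 2, and the analyses are meant to inform a full trial. Both planning quantities, the control-clinic suppression rate and the observed difference, would be affected.

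**Working it through.** The plan gives no figure to reproduce on this point, so the check is first of the wording and then of the possible size.

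**1. Which charts pass the test?** Write H for ≥400 and L for <400. List every sequence of values in the 12-month window, keep those with at least two H, and count those ending in L.

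| Values in window | Qualifying sequences | Ending in L | Ending in L if the latest must be H |
|---|---|---|---|
| 2 | 1 | 0 | 0 |
| 3 | 4 | 1 (HHL) | 0 |
| 4 | 11 | 4 | 0 |
| 5 | 26 | 11 | 0 |

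These are counts of patterns, not of patients. With exactly two values there is no gap. With three or more there is. The documents do not say how often viral load is measured.

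**2. Does other text close the gap?** The check against clinic records does not say which value counts. The resistance criteria make an HHL chart less likely, because testing is tied to failing ART, but they set no viral-load condition at enrolment. The Statistical Analysis Plan's change analyses would deal with the problem only if a baseline value were defined, and none is.

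**3. Inputs for size.** From the Intervention Pilot Test paragraph: n = 30 per clinic. (The eligibility paragraph gives 20 per clinic and 80 in total; that conflict is a separate matter to be reconciled.) All else is assumed:
- q, share of entrants re-suppressed: 5–20%
- r, their chance of suppression at follow-up: 70–90%, the same in both clinics
- p, the chance for unsuppressed entrants: 30–50%
- D, true effect in unsuppressed entrants: 10–20 points, with no effect in re-suppressed entrants

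**4. Level.** A clinic's rate rises by q × (r − p). Smallest: 0.05 × (0.70 − 0.50) = 1 point. Largest: 0.20 × (0.90 − 0.30) = 12 points.

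**5. Dilution, equal q in both clinics.** The observed difference is (1 − q) × D, so the loss is q × D. Smallest: 0.05 × 10 = 0.5 points. Largest: 0.20 × 20 = 4 points. Equal q creates no spurious difference.

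**6. Systematic difference between clinics.** With no true effect, the bias is (q₁ − q₂) × (r − p). If the clinics differ by 10 percentage points in q (3 patients in 30), it is 0.10 × 0.20 = 2 points to 0.10 × 0.60 = 6 points. The documents give no evidence that such a difference exists.

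**7. Precision.** The standard error (SE) of the clinic difference is √(2 × π(1 − π)/n), with clustering ignored and π the suppression rate. At π = 30% and n = 30 it is √(2 × 0.3 × 0.7/30) = 11.8 points. With p = 30% and r = 90%:

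| q | Rate with re-suppressed patients left in | SE, left in (n = 30) | n after restriction | SE, restricted (rate 30%) |
|---|---|---|---|---|
| 5% | 33% | 12.1 | 28.5 | 12.1 |
| 10% | 36% | 12.4 | 27 | 12.5 |
| 20% | 42% | 12.7 | 24 | 13.2 |

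Restriction gives an equal or slightly larger SE.

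**The case against.** The strongest case is that the main clause governs. It says in the present tense that patients are not suppressed, and the Intervention Pilot Test paragraph describes recruits in the same terms. Viral load is checked in clinic records before enrolment. A screener who saw a latest value below 400 would have to override the main clause to enrol that patient. On this reading the two values are evidence of current status, not a substitute for it. This is a fair account of the probable intent. It does not remove the gap, because a nurse pre-screening charts has only the parenthesis as a working test.

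Three stronger readings are tempting, and the documents do not support them.

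- A reader might infer that the plan contradicts its own statement that effects are assessed only in unsuppressed patients. That statement mainly separates unsuppressed patients from those starting treatment, who also receive guidance. It is not an analysis-set rule about re-suppression before entry. The wording is ambiguous, not contradictory.
- A reader might infer that chance imbalance in re-suppressed patients between two small clinics adds noise. With equal q, that variation is already inside the binomial sampling error (step 7), so it is not an added harm.
- A reader might infer that the plan has no baseline at all. Extraction starts at baseline and change is to be analysed, so a baseline is presupposed. What is missing is its definition.

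Two further objections stand. No affected patient has been shown to exist. And a rule on the latest value sets no recency limit: a patient with high values at 11 and 8 months before enrolment and no later test would pass it, yet may be suppressed at entry.

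**Conclusion.** The concern holds as a gap in the eligibility wording that the Statistical Analysis Plan does not catch. The stated test can admit a patient with three or more values who is already suppressed, and the outcome would then count that patient as suppressed with no baseline status to show why.

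The number of such patients is unknown and may be zero. On the assumed inputs, clinic rates rise by 1–12 points and a true difference of 10–20 points loses 0.5–4 points. That is small beside a sampling SE of about 12 points. A systematic difference between the two clinics in such patients would bias the comparison. With one clinic per arm, it would be confounded with everything else that differs between the clinics. The plan calls its analyses exploratory and disclaims power. Severity is minor.

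**What to change.** Make the parenthesis match the main clause: state that the most recent viral load on record before enrolment must be ≥400 cp/ml. Keep that value and its date as the baseline viral load, since the planned extraction begins only at baseline and may miss it. Report baseline suppression status and time since the test by clinic; the date lets a reader judge how far an old value can be trusted, which the clause alone does not settle.

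For any patients enrolled under the present wording, report the percentage suppressed at follow-up among those ≥400 at baseline, beside the all-enrolled result. Restriction is preferable to a baseline covariate: at q of 5–10% only 0.05 × 30 = 1.5 to 0.10 × 30 = 3 such patients are expected per clinic, too few to adjust on.

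The cost is one clause and one variable from records already checked. The eligible pool may shrink slightly, or the analysis set may fall to 24–28.5 of 30 per clinic. At 30% suppression the SE would then rise from 11.8 to 12.1–13.2 points (at 20 per clinic, 16–19 left, from 14.5 to 14.9–16.2). The gain is in bias and interpretability, not precision. If no such patients exist, the estimate does not change.

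### The viral load entry criterion is not tied to the regimen in use at enrolment, so patients can qualify on values from a regimen they have already left

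*Combined protocol and SAP*

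**What the plan says.** The patient eligibility paragraph under STUDY PROTOCOL sets several conditions that bear on this point.

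- **Time on treatment:** patients "are on ART and initiated ART at least 6 months prior (to have sufficient time to confirm viral load". The clock starts at first ART, not at the present regimen.
- **Viral load:** patients "are not virally suppressed (at least two viral loads ≥ 400 cp/ml within prior 12 months at time of enrollment". No minimum time on treatment, regimen or spacing is attached to the two values, and there is no explicit rule for the latest one.
- **Resistance result:** patients "do not show viral resistance in the past 6 months".
- **Resistance test:** patients are excluded "if they have not been tested for viral resistance as part of standard of care". The text explains who gets that test: "all patients failing second-line ART and some patients failing first-line ART are undergo resistance testing".
- **Record check:** viral "load and time from ART initiation will be confirmed with clinic records before enrollment". A start date for the current regimen is not among the items checked.

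For the outcome, patients' "viral loads will be extracted from medical records from baseline to 6-months post-baseline". STATISTICAL ANALYSIS PLAN states: "We will use logistic regression to examine changes in viral suppression (% suppressed at follow-up, % adherent to at least 95% of doses". It names no covariates. The Intervention Pilot Test paragraph describes one matched pair of clinics, matched on staffing, total patients and number of unsuppressed patients.

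**The concern.** The reason given for the 6-month minimum is to allow enough time to confirm viral load, which suggests that the investigators wanted qualifying values to reflect established treatment. The viral load criterion does not secure this, because its window is twice as long and ignores regimen.

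The clearest gap is a regimen change between the qualifying values and enrolment. The patient enters as unsuppressed on the strength of drugs no longer taken. If suppression follows, part of it may be due to the change and not to the treatment partner.

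Two things are at stake. The pilot's second aim includes preliminary effects on viral suppression, and the SAP says the results are to help plan a full RCT. A group whose viral load is moving for another reason blurs the suppression percentages in both clinics. Also, with one clinic per arm, any difference between the clinics in the share of such patients cannot be separated from the intervention.

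**Working it through.** The documents give no suppression rate, power or effect size, so there is no planned figure to reproduce. The window arithmetic uses document figures; the size illustrations rest on assumptions.

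**1. Windows.** Inputs: look-back 12 months, ART minimum 6 months. For a patient *t* months after starting ART:

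- pre-ART part of the look-back = max(0, 12 − *t*)
- part falling in the first 6 months of ART = min(12, *t*) − max(0, *t* − 6), floored at 0

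| Months since ART start | Pre-ART months in look-back | First-6-months-of-ART months in look-back |
|---|---|---|
| 6 | 6 | 6 |
| 8 | 4 | 6 |
| 10 | 2 | 6 |
| 12 | 0 | 6 |
| 15 | 0 | 3 |
| 18 | 0 | 0 |

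On the viral load wording alone, pre-ART values can count below 12 months of ART and early-ART values below 18 months.

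For a regimen changed *s* months before enrolment, the part of the look-back on the old regimen is max(0, 12 − *s*), whatever the total time on ART. At *s* = 2 this is 10 of the 12 months.

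**2. Routes set against the resistance rules.**

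- *Pre-ART values alone:* the patient must also have had a standard-of-care resistance test, described as done in people failing ART. This largely closes the route in practice, though not by explicit wording.
- *Early-ART values:* the patient would have to have been treated as failing, and tested, within a short time on ART. The route is narrowed, not closed.
- *Regimen since changed:* the test requirement does not block this. Take values ≥ 400 cp/ml at 11 and 9 months ago, resistance found 8 months ago, and a change after that. The values lie inside 12 months, the resistance result lies outside 6 months, and a test has been done. Every stated viral load and resistance condition is met.

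**3. Imbalance (assumed rates).** Suppose 75% of such patients suppress against 30% of the rest, with no true effect, and the counts are 6 of 30 in one clinic and 3 of 30 in the other:

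(6/30 − 3/30) × (0.75 − 0.30) = 0.10 × 0.45 = 0.045, or 4.5 points.

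With equal shares the spurious difference is 0, but 3 of 30 in each clinic would raise suppression by 0.10 × 0.45 = 4.5 points in both, from 30% to 34.5%. The eligibility paragraph elsewhere gives 20 per clinic, which conflicts with 30 and needs reconciling separately. At 20, the same 3-patient imbalance gives 3/20 × 0.45 = 6.75 points.

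**4. Dilution (assumed rates).** Let a share *f* suppress at the same rate in both clinics, and let the rest suppress at 30% (control) and 50% (intervention). The difference is (1 − *f*) × 20 points. For *f* = 0, 10%, 20% and 30% it is 20, 18, 16 and 14 points. With two-sided alpha 0.05, 80% power, no clustering and 80% suppression in the share *f*, the number per arm is 93, 119, 152 and 199. This assumes that the intervention has no effect in the share *f*.

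**The case against.** The strongest reply has five parts.

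- **The test requirement protects entry.** A reader might infer from the 12-against-6-month mismatch that patients can readily enter on values from before ART. The documents do not support that, because a resistance test given to people failing ART is also required. This stands for pre-ART values, and partly for early-ART values. It does not close the changed-regimen route.
- **Nothing shows that such patients suppress regardless.** A reader might infer that they will suppress whatever the partner does. No suppression rate is given for them, any regimen has to be taken to work, and adherence is what the intervention targets. The documents also do not say how often regimens are changed, least of all where no resistance was shown. This stands: the mechanism is plausible, its size unknown.
- **There is a concurrent control.** Equal shares give no spurious difference. This stands too, but it does not remove dilution, and matching takes no account of regimen history.
- **The illustrated bias is small beside the noise.** At 30% suppression and 30 per clinic, the standard error of the difference is √(2 × 0.3 × 0.7/30) = 0.118, about 12 points before clustering. The 4.5 points correspond to 0.045 × 30 = 1.35 patients. The SAP calls its analyses exploratory and disclaims power. This limits the weight of the point.
- **The control rate may be the right one for planning.** A full RCT with the same eligibility rule would see the same mix, so calling the pilot's control rate too high holds only if eligibility changes. This stands.

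Taking the opening words of the criterion to mean currently unsuppressed would not settle the matter either, since a value taken early on a new regimen can still be ≥ 400 cp/ml.

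**Conclusion.** The concern holds in limited form. As written, the criteria admit patients whose qualifying values come from a regimen changed before enrolment, and the stated record check would not identify them. This rests on the text and the window arithmetic alone.

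The effect on results is conditional. Inflated suppression and dilution require that such patients enrol and suppress more often for reasons other than the intervention. Bias in the clinic comparison requires, in addition, unequal shares. That is possible with one clinic per arm, but nothing in the documents shows it, and it should not be read as a demonstrated bias. The 4.5 points (6.75 at 20 per clinic) and the dilution figures only show scale under assumed rates and counts.

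This is a cheap improvement to an exploratory pilot, not a flaw that undermines its feasibility and acceptability purpose.

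**What to change.** **Eligibility.** State in the viral load criterion that both qualifying values were taken on ART, after the protocol's own minimum time on treatment, and on the regimen in use at enrolment. If the investigators judge that this shrinks the pool too far, or if enrolment is complete, leave eligibility as it is and rely on the reporting below.

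**Data and reporting, in either case.**

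- Extract the date of any regimen change from the first qualifying value up to baseline.
- Report such changes by clinic as a baseline characteristic.
- Report suppression by clinic with and without patients who changed regimen before baseline.
- Report post-baseline changes descriptively and do not exclude patients on them. The intervention could influence those changes, so excluding on them could itself bias the comparison.

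**Cost.** One eligibility sentence if the criterion is changed, with a somewhat smaller eligible pool whose reduction the documents do not allow one to estimate. The reporting needs one extra chart field, from charts that the study nurse already pre-screens; time from ART initiation is already confirmed from records.

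### The recruitment target contradicts itself: 60 dyads at 30 per clinic in two clinics, or 80 dyads at 20 per clinic, which would need four clinics

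*Combined protocol and SAP*

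**What the plan says.** The Intervention Pilot Test paragraph of the Study Protocol sets the design: "We will recruit 60 people living with HIV who are not virally suppressed and their 60 treatment partners in 1 matched-clinic pair (30 dyads/clinic". Data are collected on seven satellite clinics, and the matching step ends by "selecting one pair of matched intervention and control clinics". Randomisation is by clinic: "Clinics will be randomly assigned to standard of care or a healthcare provider guidance and treatment partner training intervention".

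The patient eligibility paragraph, later in the same protocol, gives a different target: "We will recruit 80 patients (20 per clinic; half men and half women) and their 80 treatment partners". It does not say how many clinics this covers. It is also the only place where a split by sex appears.

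The outcome text just before the eligibility criteria refers to one clinic per arm: "We will obtain viral load suppression rates for the intervention and control clinic at baseline and 12-months post-baseline". The Statistical Analysis Plan section gives no sample size and no clinic count, and says of power: "We do not expect to have sufficient statistical power to adequately examine effects".

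**The concern.** Both recruitment sentences are current, forward-looking instructions. They disagree on the total (60 or 80), on the number per clinic (30 or 20) and, by implication, on the number of clinics (2 or 4).

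Three things depend on which sentence governs:

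- **Feasibility reporting.** Feasibility is a stated purpose of the pilot. Reaching 60 dyads is full recruitment under one sentence and 75% of target (60/80) under the other.
- **The sex quota.** An even split means 10 men and 10 women per clinic at 20 per clinic. If the split carries over to 30 per clinic, it means 15 and 15.
- **The number of randomised units.** With one clinic per arm, the intervention effect is completely confounded with differences between the two clinics. With two per arm there would be at least some replication, and between-clinic variation within an arm could in principle be estimated. The two versions are therefore different designs as well as different headcounts.

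**Working it through.** **Inputs**

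| Source | Total dyads | Per clinic | Clinics |
|---|---|---|---|
| Intervention Pilot Test paragraph | 60 | 30 | 2 (one matched pair) |
| Patient eligibility paragraph | 80 | 20 | not stated |
| SAP section | not stated | not stated | not stated |

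The seven satellite clinics are the pool for matching, not the number randomised.

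**Step 1. Reproduce each figure** (total = clinics × dyads per clinic)

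- Pilot test paragraph: 2 × 30 = 60. It is internally consistent.
- Eligibility paragraph, with the two clinics of the design: 2 × 20 = 40, half the stated 80.
- Clinics needed for the eligibility paragraph to hold: 80/20 = 4, that is, two matched pairs. Only one pair is selected.

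**Step 2. Size of the gap**

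- Totals: 80 − 60 = 20 dyads, and 20/60 = 33%.
- Per clinic: (30 − 20)/30 = one third.

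**Step 3. Readings that might reconcile the two sentences**

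- *Dropout allowance.* Inflating 60 to 80 requires 60/(1 − d) = 80, so d = 25%. No dropout rate is given, and 80 in two clinics would be 40 per clinic, not 20.
- *Twenty of each sex per clinic.* This gives 2 clinics × 2 sexes × 20 = 80, but the sentence does not say that, and the result still contradicts a total of 60 and 30 per clinic.
- *Four clinics at 30 each.* This gives 120 and matches neither sentence.
- *Screened versus enrolled.* Neither sentence makes this distinction; both state how many will be recruited.

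None of these works.

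**Step 4. Effect on precision**

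For illustration, assume an observed suppression proportion of 50% (not a figure from the documents) and ignore clustering. The exact (Clopper-Pearson) 95% intervals are:

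- one clinic of 30 (15/30): 31% to 69%;
- one clinic of 20 (10/20): 27% to 73%;
- one arm of 40, as two clinics of 20 (20/40): 34% to 66%.

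The version with 20 per clinic is less precise for a single clinic. Over a whole arm, if there really are four clinics, it is slightly more precise, before any allowance for clustering. Precision therefore does not settle which version is meant.

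**The case against.** The strongest reply is that the clinic count is hardly in doubt. Four clinics is an inference from 80/20 and is never stated. Every direct statement points to two: one matched pair, one pair selected, and repeated singular references to the intervention clinic. The plural for clinics in the SAP also fits one clinic per arm. On this view the eligibility sentence is a stray figure. In addition, 40 is a hybrid of the two paragraphs that neither one plans.

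The consequences can also be called modest. The SAP describes the analyses as exploratory, disclaims adequate power and specifies no model for clustering, so no inferential claim depends on 60 or 80.

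Much of this stands. The four-clinic count is implied only, the total of 40 serves only to show that the eligibility sentence fails within the two-clinic design, and no power figure is invalidated. But these arguments show which sentence is probably wrong; they do not remove the contradiction. A site team following the eligibility paragraph would recruit to a different total and a different quota per clinic, and nothing in the document tells them not to.

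**Conclusion.** The concern holds. The protocol states two incompatible recruitment targets, 60 dyads at 30 per clinic and 80 dyads at 20 per clinic. They are 20 dyads (33%) apart in total and a third apart per clinic, and the second implies four clinics where the design has two. This is an error in a basic design quantity and must be corrected.

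The conclusion rests on the documents' own figures and simple arithmetic; only the interval widths use an assumed proportion. The two-clinic, 60-dyad version is the better supported, because it is internally consistent and agrees with the singular references to clinics elsewhere. The eligibility sentence may be left over from another design, but the documents do not say so, and the sponsor has to confirm it.

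**What to change.** **Preferred.** Restate the recruitment sentence in the patient eligibility paragraph to match the one-pair design: 60 patients, 30 per clinic with equal numbers of men and women (15 and 15), and 60 treatment partners. State the same total and the number of clinics once in the Statistical Analysis Plan section, which now gives neither. This is a one-sentence protocol correction plus one line in the SAP, with no extra patients and no change to the design.

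**If four clinics are intended.** Change the pilot test paragraph to two matched pairs at 20 dyads per clinic, and put the references to a single intervention clinic and a single control clinic into the plural. This is not free: it adds 20 dyads and two clinics to that paragraph's plan.

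In either case the sponsor should confirm which number was used in practice, so that recruitment is reported against one target.
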